9.2.3 Patient Reported Outcomes

Subjective assessments of subjects' oral symptoms will be obtained by using instruments from the NIH consensus documents for oral cGVHD, a condition that is very similar to other Oral Inflammatory Ulcerative Diseases (see Appendix 3 &4). These include report of mouth sensitivity at rest and sensitivity with stimulation (e.g. eating) on an eleven point scale. For the primary endpoint the worst sensitivity in the past week will be used. The clinician seeing the subject will

complete these forms at each study visit. Patients will also report daily sensitivity on an eleven point scale (see Appendix 2). Tolerability and compliance will also be evaluated, and a patient reported global assessment of overall improvement will be evaluated at the four-week visit.

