13.1.2 Analysis of Secondary Endpoints

Oral health related quality of life will be assessed before and after topical therapy using the 14-item Oral Health Impacts Profile (OHIP-14; see Appendix 5) instrument that measures subject's perceptions of the impact of oral conditions on their well-being. The OHIP-14 scores will be summarized descriptively for each arm at pre-treatment, post-treatment, and pre-to-post treatment change. The pre-to-post treatment change for each item and for all items combined will be assessed within each arm using either paired t test or Wilcoxon-signed-rank test depending on its distribution. In addition, each question will be dichotomized and classified as 'response' if the answer is 'not at all', or 'slightly' to a question such as "how isolated do you feel as a result of this oral condition", and pre-to-post treatment improvement will be assessed using McNemar's test within each arm.

In order to evaluate the clinical improvement in clinician-reported outcome measures for Oral Inflammatory Ulcerative Diseases, REU scores within the compound dexamethasone solution in Mucolox™ group (Arm A) will be compared to that in the dexamethasone solution only group (Arm B). The REU scores will be summarized descriptively for each arm at pre-treatment, post-treatment, and pre-to-post treatment change. The pre-to-post treatment change will be compared between the arms using either student's t-test or Mann-Whitney test, depending on the distribution of the data.

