Appendix 1**INSTRUCTIONS FOR PREPARING & USING YOUR
TOPICAL SOLUTION****WHAT YOU WILL RECEIVE**

- One 480 mL bottle of concentrated solution (5 mg/5 mL)
- 4 tablets of fluconazole 200 mg

USING YOUR SOLUTION

You will be rinsing with your solution **3 times per day**.

1. Gently shake the bottle of solution.
2. Pour 5 mL of solution into the dosing cups provided.
3. Swish the solution in your mouth for 5 minutes, then spit – DO NOT SWALLOW!
4. Do not eat or drink for 15 minutes after rinsing.

Please take one table of fluconazole once a week

CONFIDENTIAL

This document is confidential. Do not disclose or use except as authorized.

	11													
	12													
	13													
	14													

	3													
	15													
	16													
	17													
	18													
	19													
	20													
	21													
	22													
	4													

CONFIDENTIAL

This document is confidential. Do not disclose or use except as authorized.

	23																						
	24																						
	25																						
	26																						
	27																						
	28																						

CONFIDENTIAL

This document is confidential. Do not disclose or use except as authorized.

Appendix 3

DEXAMETHASONE RINSE IN MUCOLOX™ FOR THE TREATMENT OF ORAL INFLAMMATORY ULCERATIVE DISEASES

VISIT #1

Subject Name _____

[figure not shown]
[figure not shown]
Medical Record Number _____

Date of Visit _____

SUBJECTIVE DATA (Over last two weeks unless specified)

MUCOSAL PATHOLOGY

- 1. Does your mouth hurt now? Y/N
- 2. Does it hurt to swallow food or drink? Y/N
- 3. How would you rate your worst mouth sensitivity over the last week?

No sensitivity

Worst sensitivity

CONFIDENTIAL

This document is confidential. Do not disclose or use except as authorized.

[figure not shown]
[figure not shown]
4. Do you avoid any foods because they make your mouth hurt?

- 0 = Not at all
- 1 = Slightly
- 2 = Moderately
- 3 = Quite a bit
- 4 = Extremely

If “yes”, what types of foods?

- a. Spicy foods
- b. Acidic foods
- c. Salty foods
- d. Hard/crunchy/crusty foods
- e. Other:

5. Do you feel that your oral intake (what you eat) is limited by your oral condition? Y/N

Not limited at all

Severely limited

Score: _____

If “Yes”, how limited do you feel it is?

- a. Partial limitation
- b. Severe limitation

6. Have you been bothered by ulcers in the mouth?

- 0 = Not at all
- 1 = Slightly
- 2 = Moderately
- 3 = Quite a bit
- 4 = Extremely

CONFIDENTIAL

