This document is confidential. Do not disclose or use except as authorized.

OBJECTIVE DATA (REU score)

Site	Reticular area			Erythematous area			Ulcerative area			
	0	1	2	0	1	2	0	1	2	3
Upper/lower labial mucosa	0	1	0	1	2	3	0	1	2	3
Right buccal mucosa	0	1	0	1	2	3	0	1	2	3
Left buccal mucosa	0	1	0	1	2	3	0	1	2	3
Dorsal tongue	0	1	0	1	2	3	0	1	2	3
Ventral tongue	0	1	0	1	2	3	0	1	2	3
Floor of mouth	0	1	0	1	2	3	0	1	2	3
Hard palate mucosa	0	1	0	1	2	3	0	1	2	3
Soft palate/tonsillar pillars	0	1	0	1	2	3	0	1	2	3
Maxillary gingiva	0	1	0	1	2	3	0	1	2	3
Mandibular gingiva	0	1	0	1	2	3	0	1	2	3
Total										

(R: 0 = not present, 1 = present; E & U: 0 = not present, 1 = <1cm², 2 = 1 - 3cm², 3 = >3cm²)

Total Score:

Total Weighted Score:

PHOTOGRAPHS TAKEN (circle): YES NO

CONFIDENTIAL

This document is confidential. Do not disclose or use except as authorized.

Appendix 4

DEXAMETHASONE RINSE AND MUCOLOX™ FOR THE TREATMENT OF ORAL INFLAMMATORY ULCERATIVE DISEASES

VISIT #2

Subject Name _____

Medical Record Number _____

[figure not shown]
Date of Visit _____

SUBJECTIVE DATA (Over last one week unless specified)

MUCOSAL PATHOLOGY

- 1. Does your mouth hurt now? Y/N
- 2. Does it hurt to swallow food or drink? Y/N

3. How would you rate your worst mouth sensitivity over the last week?

No sensitivity

Worst sensitivity

4. Do you avoid any foods because they make your mouth hurt?

- 0 = Not at all
- 1 = Slightly
- 2 = Moderately
- 3 = Quite a bit
- 4 = Extremely

[figure not shown]
[figure not shown]
CONFIDENTIAL

This document is confidential. Do not disclose or use except as authorized.

If “yes”, what types of foods?

- a. Spicy foods
- b. Acidic foods
- c. Salty foods
- d. Hard/crunchy/crusty foods
- e. Other:

5. Do you feel that your oral intake (what you eat) is limited by your oral condition? Y/N

Not limited at all

Severely limited

Score: _____

If “Yes”, how limited do you feel it is?

- a. Partial limitation
- b. Severe limitation

[figure not shown]
6. Have you been bothered by ulcers in the mouth?

- 0 = Not at all
- 1 = Slightly
- 2 = Moderately
- 3 = Quite a bit
- 4 = Extremely

7. Rate your level of comfort while rinsing with the topical therapy:

[figure not shown]
CONFIDENTIAL

This document is confidential. Do not disclose or use except as authorized.

[figure not shown]
Score: _____

8. Rate the taste of the topical treatment:

Score: _____

9. Rate how your mouth feels since starting topical therapy:

Score: _____

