Appendix 5. OHIP-14

	Never (0)	Hardly Ever (1)	Occasionally (2)	Fairly Often (3)	Very Often (4)
FUNCTIONAL					
Have you had trouble pronouncing any words because of problems with your teeth, mouth, or dentures?					
Have you felt that your sense of taste has worsened because of problems with your teeth, mouth, or dentures?					
PHYSICAL PAIN					
Have you had painful aching in your mouth?					
Have you found it uncomfortable to eat any foods because of problems with your teeth, mouth, or dentures?					
Psychological Discomfort					
Have you been self-conscious because of problems with your teeth, mouth, or dentures?					
Have you felt tense because of problems with your teeth, mouth, or dentures?					
PHYSICAL DISABILITY					
Has your diet been unsatisfactory because of problems with your teeth, mouth, or dentures?					

Have you had to interrupt meals because of problems with your teeth, mouth, or dentures?						
PSYCHOLOGICAL DISABILITY						
Have you found it difficult to relax because of problems with your teeth, mouth, or dentures?						
Have you been a bit embarrassed because of problems with your teeth, mouth, or dentures?						
SOCIAL DISABILITY						
Have you been a bit irritable with others because of problems with your teeth, mouth, or dentures?						
Have you had difficulty doing your usual jobs because of problems with your teeth, mouth, or dentures?						
HANDICAP						
Have you felt that life in general was less satisfying because of problems with your teeth, mouth, or dentures?						
Have you been totally unable to function because of problems with your teeth, mouth, or dentures?

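### The Visit 1 and Visit 2 forms set different default recall periods (two weeks, then one week), so four symptom items are not comparable before and after treatment; the primary endpoint is not affected

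*Combined protocol and SAP*

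**What the plan says.** Appendix 3 (Visit #1 CRF) heads its patient questions "SUBJECTIVE DATA (Over last two weeks unless specified". Appendix 4 (Visit #2 CRF) heads the same questions "SUBJECTIVE DATA (Over last one week unless specified". Items 1 to 6 are worded identically on the two forms, and I found no explanation for the change of period.

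Two items carry their own period and so override the header. Item 1 asks "Does your mouth hurt now? Y/N". Item 3 asks "How would you rate your worst mouth sensitivity over the last week" on both forms. Section 9.2.3 confirms the period for the main outcome: "For the primary endpoint the worst sensitivity in the past week will be used".

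Section 13.1.2 describes the OHIP-14 analysis, which is within arm only. It then adds that "each question will be dichotomized and classified as" a response when the answer is *not at all* or *slightly*, with McNemar's test within each arm. The synopsis also lists a within-arm McNemar test, without naming the items.

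**The concern.** A pre-to-post change is interpretable only if the question covers the same length of time at both visits. A 14-day window gives a patient twice as many days on which to have had a symptom as a 7-day window. For a patient who reports whether something happened at all, or how bad it got at worst, the Visit 1 answer will tend to be worse than the Visit 2 answer even if the disease has not changed.

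A within-arm test cannot separate that artefact from a treatment effect, and the mismatch cannot be repaired once the answers have been collected. It would matter most if the McNemar rule in Section 13.1.2 is meant for these items.

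**Working it through.** The documents give no figure on recall, so there is no stated result to reproduce. The check compares the forms and then illustrates the size on assumed inputs.

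**Step 1. Which items take the header.**

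| Item | Visit 1 period | Visit 2 period | Source of period |
|---|---|---|---|
| 1 hurts now | now | now | item |
| 2 swallowing | two weeks | one week | header |
| 3 worst sensitivity (primary) | last week | last week | item |
| 4 food avoidance | two weeks | one week | header |
| 5 limited intake | two weeks | one week | header |
| 6 ulcers | two weeks | one week | header |

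The mismatch is confined to items 2, 4, 5 and 6.

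**Step 2. Whether a planned test reaches them.** The rule in Section 13.1.2 uses *not at all* and *slightly*. The OHIP-14 in Appendix 5 offers *Never* to *Very Often*. In the forms shown, *not at all* and *slightly* are answer options only on items 4 and 6. The example question in Section 13.1.2, about feeling isolated, is on neither form. The target of the rule is therefore ambiguous.

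**Step 3. Simplest illustration.** Assume a constant 5% chance per day of a bothersome day and no treatment effect. The chance of at least one such day is 1 − 0.95^14 = 0.512 over two weeks and 1 − 0.95^7 = 0.302 over one week.

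**Step 4. Exact McNemar test.** Inputs: n = 15 per arm (Section 13.2) and two-sided 0.05. The rest is assumed: no treatment effect, independent days, non-overlapping windows, a yes if any day was bothersome, and a daily risk p that varies between patients as a beta distribution with mean m and concentration c (a = mc, b = (1 − m)c; a larger c means patients are more alike).

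Write M_k = E[(1 − p)^k], the product over j = 0 to k − 1 of (b + j)/(a + b + j). Then:

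- P(yes at Visit 1, no at Visit 2) = M_7 − M_21
- P(no at Visit 1, yes at Visit 2) = M_14 − M_21

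For m = 0.10 and c = 50: M_7 = 0.499, M_14 = 0.271 and M_21 = 0.157. The two probabilities are 0.342 and 0.114. Summing the trinomial probabilities over all outcomes of 15 patients in which exact McNemar is significant towards improvement gives 13.1%. With 7 days at both visits, each probability is 0.499 − 0.271 = 0.228 and the result is 0.8%.

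False improvement (%), 14 days against 7 days:

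| Concentration c | m = 5% | m = 10% | m = 15% |
|---|---|---|---|
| 2 | 0.05 | 0.44 | 0.95 |
| 5 | 0.77 | 3.13 | 4.05 |
| 10 | 2.77 | 6.77 | 6.90 |
| 50 | 8.36 | 13.10 | 10.63 |

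With matched 7-day windows, every cell is 0.82% or less.

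The ceiling is the case of identical patients. With weekly probability q of 0.3, 0.5 or 0.7, the two-week probability is 1 − (1 − q)² = 0.51, 0.75 or 0.91, and false improvement is about 11%, 16% and 11%, against 0.7% to 0.9% with matched windows.

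**Step 5. When the effect fades.** At a mean daily risk of 30% the rate is about 1% or less, because nearly everyone says yes in both windows. If patients say yes only when bothered on at least half the days, it is at most 1.5% in the settings examined. On a scored item, assume a within-patient daily SD of 0.5 to 1.5 points and day-to-day correlation of 0 to 0.8. Reporting the worst day then gives 0.17 to 0.60 points of spurious improvement; reporting the average gives about zero.

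**Step 6. Between arms.** Both arms use the same forms, so the artefact has the same expected size in each and largely drops out of a comparison of changes.

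**The case against.** The strongest reply is that nothing planned depends on these items. Section 13 names no analysis of items 2, 4, 5 or 6. The McNemar sentence sits in the OHIP-14 paragraph, so the shared labels may only show that the rule was worded for another form. This stands to the extent that the link is conditional. It does not remove the point: as printed, either the rule reaches items 4 and 6 or its labels fit no answer on the OHIP-14.

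Second, items 2, 4 and 5 are in the present tense, and patients may answer about now whatever the header says. Only item 6, "Have you been bothered by ulcers in the mouth", looks back by its own wording. This also stands; the tilt is most plausible for item 6.

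Third, the illustration uses an any-day yes/no rule, whereas items 4 and 6 are five-level severity items and *slightly* still counts as response. The assumed daily risks also sit uneasily with patients who must score at least 7 for worst sensitivity in the past week. This is fair, and it is why no single percentage should be the headline.

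A reader might go further and infer that the OHIP-14 paired tests are biased. The documents do not support that. The same form is used at both visits, so its period does not differ between them. Its items, such as those ending "because of problems with your teeth, mouth, or dentures", show no recall statement in the text available, but one may have been lost in conversion from PDF. Any dilution from answers reaching back before treatment cannot be sized.

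**Conclusion.** The defect is certain but narrow. Followed as written, the forms ask items 2, 4, 5 and 6 over two weeks before treatment and one week after.

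Any bias runs towards apparent improvement within arm. It needs any-symptom or worst-symptom reporting, and it is about zero under average or present-moment reporting. If the McNemar rule is applied to items 4 and 6, false improvement lies between about 0% and 13% for 15 patients per arm, mean daily risk of 5% to 15%, concentration 2 to 50, independent days and an any-day rule. It approaches 16% only if patients are all alike. The comparison is at most about 1% with matched windows. None of the assumed risks comes from the documents.

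Because the primary endpoint is also a symptom change, a reader might infer that it is biased too. It is not: item 3 fixes the last week at both visits, Section 9.2.3 agrees, and Section 13.1.1 compares the change between arms. Sample size and power are unaffected. This is a correction worth making because it is nearly free and cannot be made after collection.

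**What to change.** 1. Print one week as the default recall on the Visit 1 subjective form, as Visit 2 already does. This matches the primary item. The cost is one line on one form before first use.
2. Have the SAP promised in Section 13 name the items to which the *not at all* / *slightly* McNemar rule applies. If it is meant for the OHIP-14, restate it in that form's own answer options. The cost is a sentence or two.
3. As a minor addition, check the OHIP-14 form in use. If it has no recall statement, print the same one at both visits, short enough to fall inside the treatment period at Visit 2. The small downside is reduced comparability with studies that used another period.

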Appendix 5. OHIP-14

	Never (0)	Hardly Ever (1)	Occasionally (2)	Fairly Often (3)	Very Often (4)
FUNCTIONAL					
Have you had trouble pronouncing any words because of problems with your teeth, mouth, or dentures?					
Have you felt that your sense of taste has worsened because of problems with your teeth, mouth, or dentures?					
PHYSICAL PAIN					
Have you had painful aching in your mouth?					
Have you found it uncomfortable to eat any foods because of problems with your teeth, mouth, or dentures?					
Psychological Discomfort					
Have you been self-conscious because of problems with your teeth, mouth, or dentures?					
Have you felt tense because of problems with your teeth, mouth, or dentures?					
PHYSICAL DISABILITY					
Has your diet been unsatisfactory because of problems with your teeth, mouth, or dentures?					

Have you had to interrupt meals because of problems with your teeth, mouth, or dentures?						
PSYCHOLOGICAL DISABILITY						
Have you found it difficult to relax because of problems with your teeth, mouth, or dentures?						
Have you been a bit embarrassed because of problems with your teeth, mouth, or dentures?						
SOCIAL DISABILITY						
Have you been a bit irritable with others because of problems with your teeth, mouth, or dentures?						
Have you had difficulty doing your usual jobs because of problems with your teeth, mouth, or dentures?						
HANDICAP						
Have you felt that life in general was less satisfying because of problems with your teeth, mouth, or dentures?						
Have you been totally unable to function because of problems with your teeth, mouth, or dentures?
